##### **IV.c. Research Plan.**

Patients with T2DM admitted with acute or chronic medical illnesses or for elective and emergency surgical illness or trauma would be considered candidates in this study. The goal of insulin therapy is to maintain a fasting and pre-meal BG<140 mg/dL while avoiding hypoglycemia. Diabetic patients admitted to general medical or surgery areas with a BG > 140 mg/dL and < 400 mg/dL will be randomized (using a randomization table) to:

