**IV.d. Basal Bolus Insulin Protocol.**

Patients will be started on basal bolus insulin therapy as previously reported (6; 7; 11; 13). In brief, subjects treated with insulin prior to admission will receive 80% of the outpatient insulin dose. Insulin-naïve patients will discontinue oral agents and will receive a starting total daily dose (TDD) of insulin of 0.4 U/kg/day for BG between 140-200 mg/dL and 0.5 U/kg/day for BG between 201-400 mg/dL. The starting TDD will be 0.3 U/kg/day in patients  $\geq 70$  yrs or with an eGFR < 60 ml/min. Half of TDD will be given as glargine or detemir once daily and half as meal time insulin (aspart or lispro) divided in three equal doses before meals. Insulin dose will be adjusted daily to maintain a fasting and pre-dinner BG between 100-140 mg/dL (6; 7).

Supplement insulin given as aspart or lispro will be given following a “supplemental insulin scale” protocol (6; 7; 27). Patients randomized to Group 1 will receive supplements to correct BG > 140 mg/dL, and those in Group 2 will not receive supplements except for correction of hyperglycemia (BG>260 mg/dL). Corrective doses for bedtime in group 1 will be given for BG > 220 mg/dL.

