## **V. METHODS and PROCEDURES APPLIED to HUMAN SUBJECTS:**

**V.a. Subject Population/Inclusion Criteria.** We plan to study a total of 250 male and female patients with a known history of T2DM for >3 months, age 18-80 yr, treated with either diet alone, any combination of oral antidiabetic agents, non-insulin injectables or insulin therapy. Subjects must have a BG >140 mg and <400 mg/dL without laboratory evidence of diabetic ketoacidosis (28).

**Exclusion Criteria.** Subjects with hyperglycemia without a history of diabetes, acute critical illness admitted to the ICU or expected to require ICU admission; receiving continuous insulin infusion, clinically relevant hepatic disease, corticosteroid therapy, creatinine  $\geq 3.5$  mg/dL and/or GFR <30, subjects unable to sign consent, and pregnancy which will be excluded by a urine pregnancy test.

**V.b. Study Sites:** The study will be conducted at Grady Memorial Hospital and Emory University Hospitals (EUH and EUHM).

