## **VI. CLINICAL MANAGEMENT GUIDELINES**

**V.I.a. Treatment of Hypoglycemia.** Hypoglycemia, defined as a BG level < 70 mg/dL will be treated following standard hypoglycemia protocols available at our institutions (6; 7; 29).

**V.I.b. Assessment and Monitoring of Hospital Complications and Mortality.** The research team will follow patients daily in order to determine presence of infectious and non-infectious complications. Nosocomial infections will be diagnosed based on standardized CDC criteria (30).

**VII. Data Analysis.** The primary endpoint of this study is mean fasting BG concentration between treatment groups. We set the equivalence margin in our non-inferiority hypothesis for comparing treatment effect as 18 mg/dL (1 mmol/l). Based on previous studies (6; 7), we anticipate a standard deviation of mean fasting BG~50 mg/dL. With a one-sided, two-sample t-test, 123 subjects would be required for each group to achieve 80% power to detect non-inferiority. Here we conservatively set the significance level as 0.025 to ensure sufficient power when a two-sided test is used for the primary outcome, we will perform cross-sectional analyses using one-way ANOVA or linear models, followed by repeated measures ANOVA or linear models to estimate difference between treatment groups while simultaneously examining mean fasting BG across multiple days during treatment. Similar analyses will be conducted for continuous secondary outcomes. Chi-square tests (or Fisher's Exact test), Logistic regression, and Poisson regression will be conducted to analyzed discrete secondary outcomes. A p-value of <0.05 is considered significant. We expect a very low attrition rate in the proposed study. Therefore, a total of 250

patients (125 patients per group) will be recruited in this pilot study. The proposed methods will be implemented by SAS (v9.2).

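### Optional gain: name one primary model whose confidence limit is compared with 18 mg/dL, and let it be an ANCOVA on the entry blood glucose that every patient must have

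*Combined protocol and SAP*

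**What the plan says.** Section VII sizes the trial on an unadjusted test with a margin of 18 mg/dL, an SD of 50 mg/dL and a significance level of 0.025: "With a one-sided, two-sample t-test, 123 subjects would be required for each group to achieve 80% power to detect non-inferiority". It recruits 125 per group and gives as the reason "We expect a very low attrition rate in the proposed study", without a figure.

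For the analysis itself it says "we will perform cross-sectional analyses using one-way ANOVA or linear models", "followed by repeated measures ANOVA or linear models to estimate difference between treatment groups", and adds a general p < 0.05 threshold for significance. It neither specifies nor excludes covariates. It does not say which estimate or limit is set against 18 mg/dL.

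Entry BG is a condition of eligibility in section V.a: "Subjects must have a BG >140 mg and <400 mg/dL without laboratory evidence of diabetic ketoacidosis". Section IV.c repeats it as a condition of randomization: "Diabetic patients admitted to general medical or surgery areas with a BG > 140 mg/dL and < 400 mg/dL will be randomized". Under IV.d, a BG reading also sets the starting insulin dose in patients previously on oral agents. No stated analysis uses the value.

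**The concern.** Two things are left open.

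1. **The decision rule.** The sizing test is one-sided against a margin. A standard one-way ANOVA F-test is two-sided against zero. With two arms the two share the same estimate and standard error but test different hypotheses, and a non-significant F-test is not evidence of non-inferiority. As written, the section does not tie any model to the margin.
2. **The covariate.** A baseline measurement related to the endpoint is available for every patient at no cost. If it predicts the endpoint at all, adjustment narrows the confidence interval. That has some value here, because 125 per arm is only 2 above the required 123.

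Leaving both adjusted and unadjusted models available also allows a choice between them after the data are seen, which raises the one-sided error slightly above 2.5%.

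**Working it through.** **Inputs from section VII:** margin 18 mg/dL, SD 50 mg/dL, one-sided alpha 0.025, 123 per arm required, 125 per arm recruited. **Assumptions:** true difference 0, and correlation r between entry BG and endpoint of 0.1, 0.2 or 0.3 (not in the documents).

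**1. Reproduce the plan's figure.** Power = P(T > t(0.975, df)), where T is noncentral t with df = 2n − 2 and noncentrality 18 / (50·√(2/n)).
- n = 122: 79.97%
- n = 123: 80.3%, so the stated 123 is exact
- n = 125: noncentrality 18 / (50·√(2/125)) = 18 / 6.32 = 2.85; power 80.9%

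**2. Add entry BG.** Residual SD = 50·√(1 − r²), with df = 2n − 3. Half-width of the 95% CI = 1.96 × SD × √(2/125).

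| r | Residual SD | Power at 125 per arm | Half-width (mg/dL) | n per arm for 80% | Loss per arm that 125 can absorb |
|---|---|---|---|---|---|
| unadjusted | 50.0 | 80.9% | 12.4 | 123 | 2 (1.6%) |
| 0.1 | 49.7 | 81.3% | 12.3 | 121 | 4 (3.2%) |
| 0.2 | 49.0 | 82.5% | 12.1 | 118 | 7 (5.6%) |
| 0.3 | 47.7 | 84.4% | 11.8 | 112 | 13 (10.4%) |

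If r = 0, ANCOVA still has 80.9% power at 125 per arm, so the lost degree of freedom (247 instead of 248) has no visible cost.

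**3. Attrition.** At 119 evaluable per arm (about 5% loss), power is 79.0% unadjusted, 80.6% at r = 0.2 and 82.6% at r = 0.3. At 112 per arm (about 10% loss) it is 76.5% unadjusted and 80.3% at r = 0.3.

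**4. Choosing the model afterwards.** At a true difference of 18 mg/dL, the two test statistics correlate at √(1 − r²) = 0.995, 0.980 and 0.954. If either result may be used to claim non-inferiority, the one-sided error is 0.025 + 0.025 − P(both significant). This gives 2.7%, 3.0% and 3.2% for r = 0.1, 0.2 and 0.3.

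**5. Is the covariate defined?** Not yet. For starting doses in patients on oral agents, the Group 1 text refers to BG at randomization. The Group 2 text refers to the admission and/or randomization value for the lower band, and to the admission and/or mean value for the upper band. Those passages need reconciling. For the analysis, what matters is that a covariate built from them could differ by arm.

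**The case against.** The strongest reply is that this is preference rather than defect. The unadjusted analysis reaches 80% power, and the benefit depends on an r that the documents do not give. Several features suggest that r is low. Entry BG is not stated to be fasting, it is restricted to 140–400 mg/dL, and treatment works against the link: "Insulin dose will be adjusted daily to maintain a fasting and pre-dinner BG between 100-140 mg/dL". At r = 0.2 the gain is only 1.6 points of power (82.5 − 80.9), and the error from an open model choice is at most 0.7 points above 2.5% over the range shown. All of this stands, and it keeps the point optional.

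It is also fair to say that the linear-models option may have been meant to allow covariates, since with two arms a treatment-only linear model is the one-way ANOVA. So a reader who infers that the plan rejects adjustment goes too far: covariates are unspecified, not excluded.

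Two further readings are tempting but unsupported. One is that the trial is underpowered or its analysis invalid without ANCOVA; the figures above show otherwise for an unadjusted comparison with the margin. The opposite one is that the planned primary comparison is already sound as written. The text never commits to comparing a limit with 18 mg/dL, and the p < 0.05 sentence could be applied to a test against zero.

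**Conclusion.** The point holds as a low-cost improvement, to be considered rather than required. The firm part is that section VII names no model whose limit is judged against 18 mg/dL and specifies no covariates, although entry BG exists for every patient.

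The size of the gain is conditional. It is 0.4, 1.6 or 3.5 points of power at r = 0.1, 0.2 or 0.3, and it allows 2, 5 or 11 more patients per arm to be lost before power falls below 80%. That is negligible at the bottom of the range and modest at the top. A larger r would give more, but nothing in the documents supports claiming it. The figures also assume an SD of 50 mg/dL, which section VII gives for mean fasting BG, and a true difference of zero.

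**What to change.** First settle the endpoint: section IV.b names mean daily BG, whereas section VII states "The primary endpoint of this study is mean fasting BG concentration between treatment groups". ANCOVA does not resolve that conflict. Then add to section VII:

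- One primary model: ANCOVA of each patient's endpoint on treatment and continuous entry BG.
- One definition of entry BG: a single named pre-randomization reading, used the same way in both arms.
- One decision rule: non-inferiority is concluded if the upper limit of the two-sided 95% CI for group 2 minus group 1 is below 18 mg/dL. A p-value against zero plays no part in that conclusion.
- The unadjusted difference and its 95% CI as a sensitivity analysis.

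If the sponsor prefers no covariate, naming the unadjusted model as primary with the same decision rule closes the gap and forgoes only the precision.

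The cost is a few sentences in the analysis plan and one degree of freedom. No new data are needed, and the sample size does not change.

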Currently, no RCTs have prospectively evaluated the need for corrective doses of insulin as part of a basal bolus regimen in the inpatient setting. We propose to study the safety and efficacy of the standard practice of correcting mild to moderate hyperglycemia (BG 140-260 mg/dL) before meals and bedtime in patients treated with basal bolus insulin regimen. A glucose > 260 mg/dL was picked arbitrarily. **We hypothesize that correction of mild-moderate hyperglycemia with rapid-acting insulin analogs (standard of care) will not improve glycemic control or complication rates and may increase the risk of hypoglycemia.** If supplemental insulin is not necessary to correct mild-moderate hyperglycemia, inpatient management of hyperglycemia in patients with T2DM may be simplified, may reduce the risk of hypoglycemia and save costs.

**Specific Aim: To test whether correction of mild-moderate hyperglycemia (BG > 140 mg/dL) with supplemental doses of rapid-acting insulin analogs improves glycemic control, complication rates, and rates of hypoglycemia in hospitalized patients with type 2 diabetes treated with basal bolus insulin regimen.** Patients with T2DM admitted to the hospital receiving basal bolus therapy will be randomized to receive insulin correction before meals and at bedtime for BG >140 mg/dL, while others will be followed without insulin supplementation except for severe hyperglycemia (BG > 260 mg/dL).

**Table 1:** Total and Supplemental Insulin needs in Basal Bolus Arm of RCT

Trial	Number	Mean TDD Insulin	Mean daily SSI
RABBIT 2D (7)	65	42 units/day	5 units/day
RABBIT 2 Surgery (6)	104	33 units/day	9 units/day
POC Study	206	42 units/day	6 units/day
Basal-Plus (11)	144	32 units/day	7 units/day
DEAN Trial (12)	67	57 units/day	8 units/day

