In the Rabbit-Surgery trial (Figure 3), 211 general non-cardiac surgery patients with T2DM were randomized to a basal bolus regimen with glargine once daily and glulisine before meals (n=104) or to SSRI before meals (n=107). Study outcomes included differences in daily BG levels and a composite of hospital complications including postoperative wound infection, pneumonia, respiratory failure, acute renal failure, and bacteremia. The mean daily glucose after the 1st day of BB and SSRI was 145±32 mg/dl and 172±47 mg/dl, respectively, p<0.01. BG readings <140 mg/dl were recorded in 55% of patients in basal bolus and 31% in the SSRI group, p<0.001. There were reductions with basal bolus as compared with SSRI in the composite outcome (24.3% and 8.6%, OR: 3.39 (95% CI: 1.50-7.65); p=0.003). We concluded that treatment with basal improved glycemic control and reduced hospital complications compared to SSRI in surgery patients with T2DM. The TDD of insulin in the basal bolus group was 33 units daily with 9 units/day of supplemental insulin. The basal bolus group in this study received more supplemental insulin than patients in the basal bolus arms of our other RCTs. This is likely because ~ 30% of patients in the Rabbit-Surgery trial underwent abdominal surgery and were likely

Figure 3. Postoperative Complications

[figure not shown]

Figure 4. Basal Bolus vs Basal Plus

[figure not shown]
[figure not shown]

Figure 5. BG before meals and at bedtime

[figure not shown]
[figure not shown]
NPO. These patients did not receive prandial insulin and therefore the supplemental dose may have been higher.

In the Basal Plus trial (11), we compared the effect of a daily dose of glargine with correction doses of glulisine to a standard basal bolus regimen in 300 medical and surgical patients with T2DM. We observed similar mean daily BG (Figure 4), pre-meal glucoses (Figure 5) and hypoglycemic events. There were no differences in length of hospital stay or hospital complications between patients treated with basal plus and basal bolus insulin regimen. These results indicate that a simple regimen of a daily basal dose of glargine plus correction doses with glulisine before meals (as needed) is an alternative to basal bolus insulin and results in similar glycemic control and hypoglycemia in general medicine and surgery patients with T2DM. In the basal bolus arm of the study, TDD of insulin was 32 units/day and of this only 7 units/day was given as supplemental dose.

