##### **IV.b. Primary and Secondary Outcomes:**

The primary outcome of the study is to compare differences in mean daily BG levels between patients receiving insulin supplementation for correction of hyperglycemia (BG > 140 mg/dL) compared to those without insulin supplementation except for correction of severe hyperglycemia (BG > 260 mg/dL).

Secondary outcomes include differences between treatment groups in any of the following measures: 1) mean BG before meals, bedtime and 3 AM; 2) number of BG within target; 3) number of hypoglycemia (BG < 70 mg/dl); hyperglycemia (BG > 260 mg/dL during the day or BG>350 mg/dl at bedtime); 4) daily dose of insulin; 5) length of hospital stay and mortality; 6) hospital complications (nosocomial infections, pneumonia, bacteremia, respiratory failure, and acute kidney injury [rise of serum creatinine >0.5 mg/dL (or 50%) of baseline value]), 7) hypoglycemia symptom assessment in both groups.

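### Section VII sizes the trial for non-inferiority with an 18 mg/dL margin, but no rule compares the estimated difference or its confidence limit with that margin

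*Combined protocol and SAP*

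**What the plan says.** All the statistical text stands in section VII (Data Analysis) of the combined protocol and SAP.

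- **Hypothesis and margin:** "We set the equivalence margin in our non-inferiority hypothesis for comparing treatment effect as 18 mg/dL (1 mmol/l". The margin appears only here.
- **Sizing:** "With a one-sided, two-sample t-test, 123 subjects would be required for each group to achieve 80% power to detect non-inferiority". The level is 0.025 and the anticipated SD of mean fasting glucose is about 50 mg/dL. The same passage gives 0.025 as a safeguard for the case where the primary outcome is tested two-sided.
- **Analysis:** "cross-sectional analyses using one-way ANOVA or linear models, followed by repeated measures ANOVA or linear models to estimate difference between treatment groups".
- **Criterion:** "A p-value of <0.05 is considered significant". This sentence comes after the methods for the secondary outcomes and reads as general, but it is the only criterion in the section.
- **Endpoint:** section VII says "The primary endpoint of this study is mean fasting BG concentration between treatment groups", while section IV.b says "The primary outcome of the study is to compare differences in mean daily BG levels between patients receiving insulin supplementation".
- **Study hypothesis:** Research Objectives and Specific Aims expects that correction "will not improve glycemic control or complication rates and may increase the risk of hypoglycemia". It mentions no margin.

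**The concern.** The sample size answers one question: can a worsening of 18 mg/dL without correction be excluded? The default p-value from an ANOVA or linear model answers another: do the arms differ at all? The two can disagree. With no stated rule, the basis for claiming non-inferiority could be settled after the data are seen.

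The study hypothesis adds to the risk. It is worded as an absence of improvement, so a non-significant difference could look like confirmation even when the data are compatible with an 18 mg/dL worsening.

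The endpoint conflict matters here because a decision rule must name the variable it applies to. The margin, SD and N are given only for mean fasting glucose.

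**Working it through.** **Inputs.** From section VII: margin 18 mg/dL, SD 50 mg/dL, one-sided 0.025, power 80%, 125 per arm planned. From Preliminary Data, for mean daily glucose: "The mean daily glucose after the 1st day of BB and SSRI was 145±32 mg/dl and 172±47 mg/dl, respectively, p<0.01". Assumptions of this check: a true difference of 0 for sizing (the documents state none), the same SD in both arms, and the ± figures taken as per-patient SDs.

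**1. The plan's own figure.** Normal approximation: n = 2 × [50 × (1.960 + 0.842) / 18]² = 121.1, so 122 per group. With the t distribution, power is 79.97% at 122, 80.3% at 123 and 80.9% at 125. The stated 123 reproduces. A two-sided 0.05 test to detect a difference of 18 mg/dL also gives 122 by the normal approximation, so N alone does not show which test is meant.

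**2. The two criteria at 125 per arm, SD 50.**
- SE = 50 × √(2/125) = 6.325.
- 95% CI half-width h = 1.9696 × 6.325 = 12.46 (248 df).
- Non-significant difference: |observed difference| < 12.46.
- Margin met: observed difference + 12.46 < 18, so observed difference < 5.54.
- Group 2 excesses from about 5.5 to 12.5 mg/dL are therefore non-significant but do not exclude 18.

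**3. How often this happens.** With the SE fixed and a true difference of 0: Φ(12.457/6.325) − Φ(5.543/6.325) = 0.976 − 0.810 = 0.166. Allowing for variation in the sample SD gives 16.6% at true 0 and 41.2% at true 9.

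**4. Dependence on the SD.** The gap exists when h > 18/2 = 9, that is, when the SD exceeds 9 / (1.9696 × √(2/125)) = 36.1. The last two columns give the probability of a non-significant result that does not meet the margin.

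| SD | h | Margin met if difference is below | At true 0 | At true 9 |
|---|---|---|---|---|
| 50 | 12.46 | 5.54 | 16.6% | 41.2% |
| 47 | 11.71 | 6.29 | 12.0% | 34.9% |
| 36 | 8.97 | 9.03 | 0.4% | 2.5% |
| 32 | 7.97 | 10.03 | <0.01% | <0.01% |

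At SD 32, observed excesses between about 8.0 and 10.0 mg/dL are significantly worse and yet meet the margin. At a true difference of 9 this occurs in 20.1% of trials.

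**5. Alpha.** A two-sided p<0.05 corresponds to the one-sided 0.025 used for sizing, so there is no conflict of level.

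**The case against.** The strongest reply is that the intent is plain. A non-inferiority hypothesis, a margin, a one-sided t-test and a level of 0.025 together conventionally mean an upper 95% limit below 18. The models are described as estimating a difference, and they yield the interval needed. The text never says that the null is zero difference, and the p<0.05 sentence is not tied to the primary outcome. All of this is fair. It shows that the rule could be applied, not that the plan states it. The intent is also blurred: 18 is called an equivalence margin, a two-sided test is mentioned, and section IV.b asks only for a comparison of differences.

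A reader might infer that the plan counts p>0.05 as success. At SD 50 a true worsening of 18 mg/dL would then pass 19.1% of the time instead of 2.5%. The documents do not say this, so the contrast only illustrates a possible misreading. It also depends on the SD: at SD 32, p>0.05 at a true 18 occurs in 0.7% of trials, below the 2.5% of the margin rule.

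The SD point stands too. The 16.6% and 41.2% rest on the fasting-glucose SD. If mean daily glucose is primary, the nearest spread in the documents is 32, from a basal bolus arm, and both arms here use basal bolus. The 47 comes from a sliding-scale arm, which this trial does not have. The 32 is itself from a single surgical trial. At that spread the gap is empty, but the two criteria still conflict, in the other direction.

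Finally, the endpoint conflict is a separate defect and should not add weight to this one. It matters here only because the rule cannot be written until it is resolved.

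**Conclusion.** The point holds as a missing decision rule for the primary comparison. The plan sets a margin and sizes on it, but the analysis text contains no comparison with the margin and no direction for the difference. Its only stated criterion does not answer the question that set N.

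At the protocol's own SD of 50 for fasting glucose, with equal SDs and 125 analysed per arm, the two criteria diverge in 16.6% of trials at a true difference of 0 and in 41.2% at 9. The size and direction of the mismatch depend on the SD, with the crossover near 36.

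Two stronger readings are not supported. The models are not unable to test non-inferiority, since they can produce the required CI. The sample size and alpha are not wrong either, since both are consistent with the stated hypothesis. The defect is still one to correct before analysis, because it concerns how the primary result will be judged.

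**What to change.** 1. Reconcile the primary endpoint between sections IV.b and VII.
2. State in section VII that the primary analysis estimates Group 2 minus Group 1 with a two-sided 95% CI, and that non-inferiority is declared only if the upper limit is below 18 mg/dL.
3. Name in advance the model that supplies this CI. With two groups and no covariates, the t-test, one-way ANOVA and linear model agree, so the open choice is the role of the repeated-measures model. Making that model supportive is one option, not a necessity.
4. Call 18 mg/dL a non-inferiority margin, and state that p>0.05 in a difference test is not evidence of non-inferiority.

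**Cost.** A few sentences once the endpoint is settled. If fasting glucose is kept, N and alpha are unchanged and power is 80.9% at SD 50 and a true difference of 0. If mean daily glucose is chosen, its margin and SD need their own justification.

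**Downside.** A non-significant difference alone can no longer be reported as non-inferiority. At SD 50 and a true difference of 9 mg/dL, 70.6% of trials would be non-significant but only 29.4% would meet the margin.

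### The across-days analysis of fasting glucose is too loosely specified for unequal hospital stays: two of the methods it permits would drop patients or understate the standard error

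*Combined protocol and SAP*

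**What the plan says.** Section VII states the endpoint as follows: "The primary endpoint of this study is mean fasting BG concentration between treatment groups". The analysis has two steps. In the first, "we will perform cross-sectional analyses using one-way ANOVA or linear models". The second is "followed by repeated measures ANOVA or linear models to estimate difference between treatment groups while simultaneously examining mean fasting BG across multiple days". Continuous secondary outcomes are to be analysed in a similar way.

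For the second step the plan gives no random patient effect, covariance structure, robust standard error or set of days to be analysed. It does not say which of the two steps is the non-inferiority test.

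The number of days per patient is not fixed. Section IV.b lists "length of hospital stay and mortality" among the secondary outcomes, and no section sets a treatment period or a minimum stay. Section VII expects very little attrition but gives no figure and does not mention discharge. Section VIII.b allows some patients with persistent hyperglycaemia to be moved to insulin infusion, with no rule for how their later values enter the analysis.

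Section IV.b names a different primary measure: "The primary outcome of the study is to compare differences in mean daily BG levels". That mismatch is a separate matter. The present point follows section VII and concerns fasting glucose, but the same reasoning would apply to mean daily glucose.

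**The concern.** Daily glucose values from one patient are correlated, and patients will contribute series of different length. A method for such data must keep patients with short series and must not count each patient-day as independent information. The planned wording guarantees neither.

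- Classical repeated measures ANOVA needs a complete row per patient, so anyone discharged before the last analysed day drops out. That costs power. If stay is related to glucose or to treatment arm, it is also a selection made after randomisation.
- A linear model fitted to patient-days as if independent gives a standard error that is too small when the within-patient correlation is positive. In a non-inferiority trial this makes the hoped-for conclusion too easy to reach.

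Because the deciding step is not named, the choice among these methods could be made after the data are seen.

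**Working it through.** **Inputs from section VII.** Margin 18 mg/dL; SD of mean fasting glucose 50 mg/dL ("we anticipate a standard deviation of mean fasting BG~50 mg/dL"); one-sided alpha 0.025; power 80%; 123 per group required, 125 planned. **Assumed, because the documents give no figure:** 3 to 7 days per patient, within-patient correlation 0.2 to 0.6, and the share of patients with a complete window.

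**1. The plan's own figure.** With a true difference of 0, n per group = 2(1.960 + 0.842)² × 50² / 18² = 2 × 7.85 × 2500 / 324 = 121.1, so 122 by the normal approximation. By the noncentral t, power is 0.7997 at 122 and 0.8029 at 123. The stated 123 is reproduced. Power with 125 per group is 0.809. This calculation uses one value per patient.

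**2. Complete-case repeated measures ANOVA.** Hold the SD of the patient mean at 50 and reduce n. The standard error of the difference is 50 × √(2/n); power is by the noncentral t.

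| Kept | n per arm | SE (mg/dL) | Power |
|---|---|---|---|
| 100% | 125 | 6.32 | 0.81 |
| 80% | 100 | 7.07 | 0.72 |
| 60% | 75 | 8.16 | 0.59 |
| 40% | 50 | 10.00 | 0.43 |

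As an illustration of retention, if stay is 2 days plus a Poisson count with mean 3 (capped at 12), about 58% of patients have at least 5 days.

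**3. Linear model on patient-days, correlation ignored.** With m days per patient and exchangeable correlation ρ, the design effect is D = 1 + (m − 1)ρ. The reported SE is 1/√D of the true one, and the actual one-sided error at the margin is 1 − Φ(1.96/√D).

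| m | ρ | D | Reported/true SE | One-sided error |
|---|---|---|---|---|
| 3 | 0.2 | 1.4 | 0.85 | 0.049 |
| 3 | 0.6 | 2.2 | 0.67 | 0.093 |
| 5 | 0.4 | 2.6 | 0.62 | 0.112 |
| 5 | 0.5 | 3.0 | 0.58 | 0.129 |
| 7 | 0.2 | 2.2 | 0.67 | 0.093 |
| 7 | 0.6 | 4.6 | 0.47 | 0.180 |

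**4. Simulation with unequal stays.** 125 per arm, stays as in step 2, stay unrelated to glucose, SD 50 for a single day's value, true difference 18, 4,000 trials per setting. The Monte Carlo standard error at 0.025 is √(0.025 × 0.975 / 4000) = 0.0025.

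| ρ | Patient-days as independent | One mean per patient | Cluster-robust SE | Complete cases, 5 days |
|---|---|---|---|---|
| 0.2 | 0.084 | 0.029 | 0.026 | 0.023 |
| 0.4 | 0.117 | 0.024 | 0.026 | 0.029 |
| 0.6 | 0.151 | 0.025 | 0.026 | 0.026 |

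Only the independence analysis departs clearly from 0.025. When stay is unrelated to glucose, complete-case analysis costs power but does not inflate the error.

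The power loss depends on what the 50 mg/dL describes. In the same simulation at a true difference of 0 (1,000 trials per setting), where 50 is the SD of a single day's value, complete-case power was 0.95, 0.82 and 0.74 for ρ of 0.2, 0.4 and 0.6. With one mean per patient it was 0.997, 0.97 and 0.93. Section VII attaches the 50 to mean fasting glucose, so step 2 follows the plan more closely.

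**The case against.** The strongest reply is that the plan does not commit to either poor method. In the sentence as built, the words repeated measures may govern both ANOVA and linear models, and the stated purpose is longitudinal. A repeated-measures linear model with a modelled covariance keeps short-stay patients and gives a valid standard error, and SAS can fit one. This stands. A reader might infer that the plan will discard patients or will ignore the correlation, but the text supports neither as a certainty.

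Secondly, the cross-sectional step comes first and matches the sample size calculation, a two-sample t-test with one value per patient. If it carries the non-inferiority test, the inflated error belongs to a follow-up analysis. This also stands: a reader might take 5-18% as the trial's false non-inferiority rate, and the documents do not show that. Nor do they name the first step as decisive.

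Thirdly, a reader might infer that dropping short-stay patients biases the result toward non-inferiority. That needs a link between stay and glucose or arm. The opening section on objectives says treatment of hyperglycaemia is associated with shorter stay, which suggests such a link. The preliminary data report no difference in stay between the arms of the basal-plus trial. Bias is possible but not established.

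Finally, a mixed model is not the only remedy. Patient means or cluster-robust standard errors kept the error near nominal in step 4. What remains of the concern is that the wording lets a valid analysis and two poor ones stand side by side.

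**Conclusion.** The point holds as a defect of specification. Section VII offers methods for repeated daily glucose without the elements that would make them suit unequal stays, and leaves open which step decides non-inferiority. Under one permitted reading, power falls from 0.81 to between 0.72 and 0.43 when 80% to 40% of patients have complete data, with SD 50 per patient mean. Under another, the one-sided error rises from 2.5% to about 5-18%, for an assumed 3-7 days and correlation 0.2-0.6. Under a third, a repeated-measures model with a modelled covariance, neither problem arises. The planned 125 per arm needs no change, and a first-step comparison of one mean per patient has a sound standard error. The sponsor should make the change, because an understated standard error would favour the conclusion the trial hopes to reach.

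**What to change.** In section VII, replace the choice between repeated measures ANOVA and linear models with one named analysis: a linear mixed model on all available treatment days of every randomised patient. Fixed effects should be treatment, day and baseline glucose, with a random patient effect or a stated covariance structure. Define which days count, and say how values after discharge or after a switch to infusion are treated. The model still assumes that discharge depends only on recorded glucose and the covariates in it; say so.

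Then state whether this model or the comparison of one mean per patient, also adjusted for baseline glucose, decides non-inferiority against the 18 mg/dL margin. The other becomes supportive.

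The cost is wording and minor analysis work. Entry already requires a glucose value, so baseline glucose is available. Sample size and data collection do not change.
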